#### **Primary outcome measure (endpoint):**

- Growth rate of the area of atrophic lesions between baseline and 24 months, as measured on fundus autofluorescence (FAF) imaging and verified by optical coherence tomography (OCT).

Methods of data analysis will be detailed in a Statistical Analysis Plan (SAP) prior to the performance of unmasked analyses. The SAP shall supersede this protocol in case of discrepancies with the SAP related to the choice of endpoints, power calculations, and statistical analyses. The SAP shall also be submitted to the regulatory agencies before any unmasked analyses are performed.

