#### *1.7.2.7 Safety Evaluations*

Based upon vitamin A's known safety and tolerability profile, possible AEs of interest have been identified and will be monitored during this study (see section [1.5.8.1](#)). Safety data will be acquired by: 12-lead ECG, physical exam, ocular exams, retinal photographs, clinical laboratory tests, bioanalytical tests (vitamin A), BCVA.

To make sure that any potential for hypervitaminosis A is detected, *symptoms* such as headaches, nausea, dry lips, dry skin, *signs* such as papilledema (optic disc swelling), and clinically meaningful abnormalities

in clinical laboratories will be explored (see section 1.16.1.6). In addition, levels of retinol, retinoic acid, and retinyl esters will be measured periodically. In order to avoid study unmasking, such data will be reviewed by the SMC. See section below on pharmacokinetic evaluations.

Vitamin A-related adverse reactions are usually reversible upon discontinuation of the vitamin.

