#### 1.7.2.8 *Pharmacokinetic Evaluations*

Plasma will be collected to measure compliance and further assess the pharmacokinetic profile of ALK-001, how it might be influenced by dietary vitamin A intake, how it fluctuates over a 2-year period as liver stores are turned over, and how the percentage of deuterated vitamin A in the blood might be linked to the progression of GA.

Metabolites of vitamin A measured in this study: ALK-001 is expected to replace existing, non-deuterated vitamin A. Total vitamin A in the plasma will be approximated by the sum of retinol + retinyl palmitate. Levels of deuterated retinyl palmitate peak 4 hours following administration of one ALK-001 dose then rapidly return close to baseline levels 24 hours post-dosing. Levels of deuterated retinol increase more slowly to peak 8-12 hours following dosing and decrease more slowly over time. Retinoic acid, another vitamin A metabolite with direct function on vision, will be measured. The absolute levels and percentage deuteration of retinol, retinyl palmitate and retinoic acid will also be measured. Percentages are calculated as the ratio between the deuterated analyte and the total amount of each analyte. Total amounts of each analyte will be calculated as the sum of the deuterated and the non-deuterated analyte. Absolute levels above the upper limit of normal may not indicate toxicity in the absence of clinical signs or other clinically meaningful laboratory abnormalities.

Levels of each analyte are expected to remain below the following upper limit of normal, determined based on a review of the literature:

Analyte (total deuterated + non-deuterated)	Approximate upper limit of normal
Retinol	1,500 ng/mL
Retinyl palmitate (random)	5,000 ng/mL
Retinyl palmitate (12+ hour after dosing)	500 ng/mL
Retinyl palmitate (24+ hour after dosing)	200 ng/mL
Retinoic acid (random)	5 ng/mL

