2.2.4 Safety and Pharmacokinetics Endpoints

- Adverse events (AEs), including serious adverse events (SAEs)
- Laboratory tests (hematology, biochemistry, lipids)
- Vital signs
- 12-lead electrocardiography (ECG)
- Physical examination
- Ocular exam and intraocular pressure (IOP)
- Pharmacokinetics: absolute concentration and percentage of deuterated vitamin A in plasma

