8.0. PHARMACOKINETIC ANALYSIS

Pharmacokinetics of ALK-001 over time when administered daily for 24 months will combine measures of absolute concentrations and percentage replacement with deuterated forms of vitamin A (as the sum of retinol and retinyl palmitate), retinol, and retinyl palmitate in plasma (required at all in-person visits except V02).

Pharmacokinetic measures include the following:

- Deuterated retinol as a fraction of total retinol
- Deuterated retinyl palmitate as a fraction of total retinyl palmitate
- Deuterated vitamin A as a fraction of total vitamin A, where vitamin A is computed as the sum of retinol and retinyl palmitate
- Other tested deuterated vitamin A metabolite(s) as a fraction of total vitamin A metabolite(s)
- Absolute concentrations (ng/mL) for each of the above analytes

Descriptive statistics for values and changes from baseline will be summarized for pharmacokinetic measures by treatment arm and visit (where a blood sample collection is performed).

The mean for pharmacokinetic parameters \pm the standard error will be plotted over time by treatment group.

The following method will be used to handle measurements that are below quantification limits (BQL):

- For subjects randomized to ALK-001:
 - At V01 (Screening) or V02 (Day 1), BQL deuterated values will be set to 0 and non-deuterated values will be set to the lower limit of quantification (LLOQ).
 - At visits other than V01 (Screening) or V02 (Day 1), all BQL values will be set to LLOQ.
- For subjects randomized to placebo:
 - BQL deuterated values will be set to 0 and BQL non-deuterated values will be set to LLOQ.

All PK analyses will be conducted in the PK Analysis Set using the above methods, on values provided by the lab while handling BQL values mentioned above, as well as on extrapolated values.

A listing of pharmacokinetic measures will be provided.

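### The vitamin A tables give no by-arm count of subjects above the protocol's upper limits and take no account of hours since dose

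*SAP*

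**What the plan says.** Protocol v1.1 section 1.7.2.7 has retinol, retinoic acid and retinyl esters measured periodically as part of the watch for hypervitaminosis A, and adds: "In order to avoid study unmasking, such data will be reviewed by the SMC".

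Section 1.7.2.8 introduces a table of limits: "Levels of each analyte are expected to remain below the following upper limit of normal". The limits apply to total (deuterated plus non-deuterated) analyte, in ng/mL:

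- retinol: 1,500
- retinyl palmitate: 5,000 (random), 500 (12+ h after dosing), 200 (24+ h after dosing)
- retinoic acid: 5 (random)

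The reason that timing matters is given in the same section: "Levels of deuterated retinyl palmitate peak 4 hours following administration of one ALK-001 dose then rapidly return close to baseline levels 24 hours post-dosing".

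The SAP's endpoint (section 2.2.4) is "Pharmacokinetics: absolute concentration and percentage of deuterated vitamin A in plasma". For it, section 8.0 plans this: "Descriptive statistics for values and changes from baseline will be summarized for pharmacokinetic measures by treatment arm and visit". Mean plots and a listing complete the output. SAP section 4.1 defines the statistics for a continuous measure as n, minimum, Q1, median, mean, Q3, maximum and SD. Neither section mentions the 1.7.2.8 limits or hours since dose.

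Elsewhere the SAP does count subjects beyond cut-offs: low/normal/high categories and liver-enzyme multiples in section 7.3, and QTcF thresholds in section 7.5. Section 7.3 covers chemistry, hematology and lipids, and Appendix 2 lists no vitamin A analyte.

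**The concern.** ALK-001 is itself a form of vitamin A, and the protocol gives the purpose of this part of the safety assessment as "To make sure that any potential for hypervitaminosis A is detected". A reader of the final report will want to know how many subjects in each arm had a level above its limit, and whether the same subjects stayed above it. The planned tables do not answer either question directly.

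Retinyl palmitate has a further difficulty. Protocol v1.1 lets subjects take the capsule before a visit (section 1.4.1), and section 1.9.2 has no instruction to hold the dose until after the draw, so hours since dose will vary. If all samples at a visit are summarised together, a higher ALK-001 value may mean only that the capsule was taken that morning.

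The adverse event tables cannot supply the missing count. Under sections 1.9.7.1 and 1.9.7.2, sites see bioanalytical data masked to treatment and subject ID. An investigator therefore cannot ordinarily link a high level to a subject and record it as an event.

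**Working it through.** The plan states no figure to reproduce. The check is what the planned statistics would and would not reveal.

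**Arm sizes.** SAP section 3.1 gives 200 subjects randomized 2:1: 200 × 2/3 ≈ 133 on ALK-001 and 67 on placebo. SAP section 3.2 takes 80% as completing: 0.8 × 200 = 160, or about 107 and 53 at Month 24.

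**Retinol (one limit, 1,500).** There are two cases at each visit.

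- Maximum at or below 1,500: the table shows that nobody was over.
- Maximum above 1,500: at least one subject was over, and the number is open. If Q3 is at or below the limit, Q3 caps it. With the SAS default quantile definition, 133 × 0.75 = 99.75, so Q3 is the 100th ordered value and at most 33 lie above it. For n = 107, 80.25 makes it the 81st value, and at most 26 lie above.

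Mean and SD tighten the cap through the one-sided Chebyshev (Cantelli) inequality: share over ≤ s² / (s² + (1,500 − mean)²), with s² = SD² × (n − 1)/n. The documents give no mean or SD, so I assume a range.

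| Assumed mean | n = 133, SD 150 / 200 / 250 | n = 107, SD 150 / 200 / 250 |
|---|---|---|
| 400 | 2 / 4 / 6 | 1 / 3 / 5 |
| 500 | 2 / 5 / 7 | 2 / 4 / 6 |
| 600 | 3 / 6 / 9 | 2 / 4 / 7 |

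For example, with mean 600, SD 250 and n = 133: s² = 62,500 × 132/133 = 62,030; 62,030 / (62,030 + 810,000) = 0.0711; × 133 = 9.46, so at most 9.

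As an illustration only, constructed samples of 133 that agree on all eight planned statistics (n 133, min 250, Q1 423, median 502, mean 525, Q3 570, max 1,600, SD 219) can have 1, 2, 4 or 5 subjects over.

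**Retinyl palmitate (three limits).** The ratio of the largest to the smallest limit is 5,000 / 200 = 25. A value of 1,000 is within the random limit but five times the 24+ h limit. Without timing, the table settles two cases: a maximum of 200 or less (nobody over) and a maximum above 5,000 (at least one over).

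Again as illustration only, take 133 constructed ALK-001 values with min 40, Q1 97, median 145, mean 176, Q3 191, max 466 and SD 112. Of these, 33 exceed 200 and none exceeds 500.

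- If those 33 were drawn within 24 h of dosing, 0 subjects are over.
- If all values were drawn at 24 h or later, 33 are over (33/133 = 24.8%).

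The eight statistics are identical in both cases. The corresponding range for 107 ALK-001 subjects at Month 24 is 0 to 26. I give no such range for placebo, because the documented 4 h peak is for deuterated retinyl palmitate after an ALK-001 dose.

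**The case against.** The strongest reply is that nothing in the documents requires this count. Protocol section 1.15.8 asks only that concentrations and percent deuterated be summarised, which SAP 8.0 does. The limits are approximate, come from a literature review and are phrased as an expectation. The protocol also cautions: "Absolute levels above the upper limit of normal may not indicate toxicity in the absence of clinical signs". Threshold counts are not a uniform SAP rule either, since vital signs and IOP get descriptive statistics alone. All of this stands, and it is why the point is an improvement and not an error.

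A second reply is that the values will be available. SAP 4.1 and 8.0 promise by-subject listings, from which retinol counts and persistence can be worked out by hand, and the visit maximum settles some cases. That also stands, so it would be wrong to say that the report hides high levels. It is weaker for retinyl palmitate: the SAP does not say that the listing carries hours since dose, and a reader may be unable to classify a value without them.

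Three stronger readings may tempt a reader, and the documents do not support them.

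- An endpoint goes unreported. Protocol section 1.6.2 does list clinically significant findings on vitamin A tests, but such a finding is not the same as a value above a limit. Section 1.6.1 also provides: "The SAP shall supersede this protocol in case of discrepancies with the SAP related to the choice of endpoints, power calculations, and statistical analyses". Section 8.0 delivers the endpoint that the SAP itself sets.
- Subjects are less well protected. Symptoms, signs and routine laboratory abnormalities are captured and tabulated by arm (SAP 7.2 and 7.3), and the Safety Monitoring Committee reviews the levels.
- Many subjects will be above a limit. Protocol section 1.5.7.3 reports earlier averages within normal ranges, so counts may be low; averages do not give a count either way.

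Finally, that the SAP combines samples across hours since dose is inferred from its silence; no instruction says so.

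**Conclusion.** The point holds as a gap in final safety reporting. The planned tables do not give the number of subjects per arm above a 1.7.2.8 limit unless the visit maximum is at or below it, and the retinyl palmitate summary cannot be read against the 12+ h or 24+ h limits. Efficacy testing, committee review and subject protection are unaffected.

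Its size in this trial is unknown, because no document gives concentrations. The retinol ceilings (2 to 9 of 133, 1 to 7 of 107) rest on assumed means of 400 to 600 and SDs of 150 to 250. The retinyl palmitate range (0 to 33 of 133) rests on a constructed sample. Both show what the table leaves open and predict nothing. The conclusion about timing assumes that the SAP means what it appears to mean: one summary per arm and visit, with no split by hours since dose.

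The change is worth making because it is cheap and serves the purpose for which the protocol has these levels measured.

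**What to change.** Add to SAP 8.0, or to the clinical study report if the SAP is closed:

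- **Table.** In the PK Analysis Set by actual treatment, n (%) of subjects above the 1.7.2.8 limit for total retinol, retinyl palmitate and retinoic acid: at any post-baseline sample, at two or more samples, and by visit.
- **Denominator.** Subjects with at least one evaluable post-baseline sample. This condition is needed because a screening sample alone meets the assessment requirement of the set in SAP 4.5. Four subjects over would be 3.7% of 107 sampled but 3.0% of 133 if unsampled subjects were counted.
- **Timing of retinyl palmitate.** Class by recorded hours since dose: under 12 h against 5,000; 12 to under 24 h against 500; 24 h or more against 200. Where hours are missing use 5,000, and report how many samples that covers. Apply the same classes to placebo only for a like-for-like comparison, with a note that capsule timing has no documented effect on placebo levels.
- **Listing.** Show hours since dose and an over-limit flag.
- **Footnote.** The limits are approximate, and exceedance alone may not indicate toxicity.

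The cost is one or two tables and additions to the listing. The concentrations are already measured. Protocol sections 1.9.2, 1.12.29 and 1.12.30 ask sites to record time since last dose, but the documents do not confirm that the field is in the database; that should be checked first. Some exceedances will have no clinical meaning. The placebo background will be imprecise: the exact two-sided 95% upper bound is 1 − 0.025^(1/67) = 5.4% for 0 of 67, and 1 − 0.025^(1/53) = 6.7% for 0 of 53.

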9.0. INTERIM ANALYSIS

No interim safety/efficacy analysis was planned or performed in the study.

Appendix 1: Assessments and Visit Schedule

Period	Screening/Baseline and Run-in ¹⁵ Period	Initial Treatment Period												24 mo End of Study	Early Termination ¹³	
		Day 1 Start of Treatment	Day 2-3 mo	3 mo	3-6 mo	6 mo	6-9 mo	9 mo	9-12 mo	12 mo	12-15 mo	15 mo	15-18 mo	18 mo		
Study Months (m)	between approx. 20 and 40 days before day 1															
Visit Window		V01	V02	Screening end/ Baseline/ Randomization	Phone Follow-up	V03	Phone Follow-up	V04	Phone Follow-up	V05 ¹² (Optional)	Phone Follow-up	V06	Phone Follow-up (Optional)	V07 ¹²	Phone Follow-up	V08
Visit (V) #																
Screening Period																
Informed Consent	-	●														
Size 0 Capsule Swallow Test	-	○														
Demographics	-	●														
Clinical Diagnosis	-	●														
Medical, Surgical and Ocular History	-	●														
Collection of Historical Retinal Images	-	●														
Vitamin A Information, counseling & Quiz ⁸	-	●														
Eligibility (Inclusion/Exclusion) Criteria	-	●														
General Health																
Prior and concomitant medications	-	●														
Treatment Emergent Adverse Events (AE) and SAEs	-	●														
Check-up phone calls	-	●														
Study Drug Reconciliation	-							●								
Visual signs	-	●						●								
12-Lead ECG	93005	●														
Physical Exam or Assessment ¹	93996	●								●						
Eye Exam ²	92014	●								●						
Quality of Life and Visual Function																
Visual Acuity (ETDRS-BCVA) ²	92015	●						●								
Low Luminance Visual Acuity (LLVA) ²	99173	●						●								
Reading Speed (REST, MINITAB) ²	-	●						●								
Vision Questionnaires (VF14, FRI)	-	●						●								
Ocular Imaging																
Color Fundus Photograph (CP) ²	92250	●							●							
OCT Angiography (OCTA) or Fluorescein Angiogram (FA) ²	92124 or 92235	●							●							
Fundus Autofluorescence (FAF) ²	92250	●							●							
Spectral Domain OCT (SD-OCT) ²	92134	●							●							
Treatment																
Treatment of ChV ¹⁶	67028	ACI / RC	ACI / RC	ACI / RC	ACI / RC	ACI / RC	ACI / RC	ACI / RC	ACI / RC	ACI / RC	ACI / RC	ACI / RC	ACI / RC	ACI / RC	ACI / RC	ACI / RC
Psychophysical function																
Microperimetry ²	92083	●							●							
Clinical laboratory (Central Lab)																
Biochemistry ³	-	●							●							
Hematology ⁴	-	●							●							
Lipids ⁵	-	●							●							
Glucose ¹⁴	-	●							●							
Vitamin A and Pharmacokinetics (PK) ⁶	-	●							●							
Complement ¹⁷	-															
Genotype ⁷	-															
Pregnancy Test ⁷	-															
Miscellaneous																
Randomization	-								●							
Drug Dispensing ⁹	-								●							

● Protocol Procedure O: Optional ACI/RC: Perform As Clinically Indicated or for Routine Care

- 1 Comprehensive physical exam (C) or simplified physical exam (S) when performed by PI or delegated personnel; Limited physical assessments when performed off-site by a home nurse.
- 2 Both eyes.
- 3 Biochemistry (CMP panel, fasting): Sodium, Potassium, Chloride, Bicarbonate, Urea, Creatinine, Calcium, Total Protein, Bilirubin, Albumin, Alkaline phosphatase, AST, ALT
- 4 Hematology (differential, fasting): WBC, neutrophils, lymphocytes, monocytes, eosinophils, basophils, RBC, HGB, HCT, MCV, MCH, PLT
- 5 Lipids (fasting): total cholesterol, triglycerides, HDL, LDL
- 6 Collect approx. 6 mL of blood, extract plasma (~ 2 x 1.5 mL), store at below -20°C in provided glass vials, ship in bulk upon request by sponsor.
- 7 Optional. As determined by the PI.
- 8 Self-administered short quiz to ensure subject understands the instructions
- 9 Investigator may dispense the appropriate number of bottles until the next visit (usually 3 or 6 bottles). At screening, a bottle containing placebo is dispensed to check subject's proper compliance at V02. Check numeral 15.
- 10 This final, exit visit shall occur 3 months after permanent discontinuation of the study drug or completion of the treatment period
- 11 Reasonable exceptions may be granted by sponsor if such exception would not be expected to influence data collection or continuous treatment of the study subject
- 12 Optional procedures performed if visit is done in person. Upon investigator's decision and if the subject does not have ongoing adverse events that are possibly associated with the study drug, this visit can be replaced by a phone call. Study drug is then directly shipped to the subject and in person assessments are not performed.
- 13 Perform optional procedures only if the early termination visit occurs at least 3 months following one of the major visits (in grey background): V04, V06, V08 and V10. Ask sponsor if unsure.
- 14 Glucose (fasting): HbA1C
- 15 Run-In period: all screen subjects may start receiving placebo for approximately 4 weeks to measure compliance. Only those subjects with greater than 80% adherence during the run-in period will be randomized
- 16 Proceed according to the PI's standard of care.
- 17 Genotype and complement can be measured at any time during the study upon sponsor's request. This will be done through central labs.

Appendix 2: Laboratory Tests for Chemistry, Hematology and Lipid Panel

Chemistry: 
• Alkaline phosphatase• Alanine aminotransferase (ALT)• Aspartate aminotransferase (AST)• Total Bilirubin• Blood urea nitrogen (BUN)• Creatinine• eGFR (CKD-EPI)• Glucose• Calcium• Protein - total• Albumin• Sodium• Potassium• Chloride• Bicarbonate	Hematology: 
• Hemoglobin• Hematocrit• Red blood cells (RBC)• White blood cells (WBC)• Neutrophils (absolute, %)• Lymphocytes (absolute, %)• Monocytes (absolute, %)• Eosinophils (absolute, %)• Basophils (absolute, %)• MCV• MCH• Platelet count
	Lipid Panel: 
• Total Cholesterol• Triglycerides• HDL• LDL

ALK001-P3001 (SAGA) SAP

Final Audit Report

2024-06-21
